  - Myocardial infarction within the last 6 months, documented by persistent elevated cardiac enzymes or persistent regional wall abnormalities on assessment of LVEF function
  - History of documented congestive heart failure (New York Heart Association functional classification III-IV)

- Documented cardiomyopathy
12. Patient has poorly controlled diabetes mellitus or steroid-induced diabetes mellitus
  13. Other concurrent severe and/or uncontrolled concomitant medical conditions (e.g., active or uncontrolled infection) that could cause unacceptable safety risks or compromise compliance with the protocol
    - Significant symptomatic deterioration of lung function. If clinically indicated, pulmonary function tests including measures of predicted lung volumes, DLco, O2 saturation at rest on room air should be considered to exclude pneumonitis or pulmonary infiltrates.
  14. Impairment of gastrointestinal (GI) function or GI disease that may significantly alter the absorption of BKM120 (e.g., ulcerative diseases, uncontrolled nausea, vomiting, diarrhea, malabsorption syndrome, or small bowel resection). Patients with unresolved diarrhea will be excluded as previously indicated
  15. Patients who are currently receiving treatment with medication with a known risk to prolong the QT interval or inducing Torsades de Pointes and the treatment cannot either be discontinued or switched to a different medication prior to starting study drug. Please refer to Table 18 for a list of prohibited QT prolonging drugs with risk of Torsades de Pointes.
  16. Patients receiving chronic treatment with steroids or another immunosuppressive agent.
    - **Note:** Topical applications (e.g. rash), inhaled sprays (e.g. obstructive airways diseases), eye drops or local injections (e.g. intra-articular) are allowed. Patients with previously treated brain metastases, who are on stable low dose corticosteroids treatment (e.g dexamethasone 2 mg/day, prednisolone 10 mg/day) for at least 14 days before start of study treatment are eligible.
  17. Patients who have taken herbal medications and certain fruits within 7 days prior to starting study drug. Herbal medications include, but are not limited to St. John's wort, Kava, ephedra (ma huang), ginkgo biloba, dehydroepiandrosterone (DHEA), yohimbe, saw palmetto, and ginseng. Fruits include the CYP3A inhibitors Seville oranges, grapefruit, pummelos, or exotic citrus fruits.

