  18. Patients who are currently treated with drugs known to be moderate and strong inhibitors or inducers of isoenzyme CYP3A, and the treatment cannot be discontinued or switched to a different medication prior to starting study drug. Please refer to Appendix B for a list of prohibited inhibitors and inducers of CYP3A (Please note that co-treatment with weak inhibitors of CYP3A is allowed).
  19. Patients who have undergone major surgery  $\leq 2$  weeks prior to starting study drug or who have not recovered from side effects of such therapy.
  20. Patients who are currently taking therapeutic doses of warfarin sodium or any other coumadin-derivative anticoagulant.
  21. Women who are pregnant or breast feeding or adults of reproductive potential not employing an effective method of birth control. Double barrier contraceptives must be used through the trial by both sexes. Oral, implantable, or injectable contraceptives may be affected by cytochrome P450 interactions, and are therefore not considered effective for this study. Women of child-bearing potential, defined as sexually mature women who have not undergone a hysterectomy or who have not been naturally postmenopausal for at least 12 consecutive months (i.e., who has had menses any time in the preceding 12 consecutive months), must have a negative serum pregnancy test  $\leq 72$  hours prior to initiating treatment.
    - Women are considered post-menopausal and not of child bearing potential if they have had 12 months of natural (spontaneous) amenorrhea with an appropriate clinical profile (e.g. age

appropriate, history of vasomotor symptoms) or six months of spontaneous amenorrhea with serum FSH levels > 40 mIU/mL [*for US only*: and estradiol < 20 pg/mL] or have had surgical bilateral oophorectomy (with or without hysterectomy) at least six weeks ago. In the case of oophorectomy alone, only when the reproductive status of the woman has been confirmed by follow up hormone level assessment is she considered not of child bearing potential.

- Women of child-bearing potential, defined as all women physiologically capable of becoming pregnant, must use highly effective contraception during treatment and for 4 weeks after stopping treatment.
- The highly effective contraception is defined as either:

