#### **5.3 Dose Escalation and Stopping Rules**

The dose-limiting toxicity (DLT), as defined in Section 5.5, will be the basis for determining the maximum tolerated dose (MTD). Any subject who receives at least one dose of the study drug (BKM120) will be included in analysis for DLT. Treatment cohorts will be dosed in escalating order, as outlined in Table 8, only after the safety of the previous dose level has been established, or until an MTD has been determined.

Subsequent dose levels will be opened for treatment as follows:

1) Escalation to the subsequent dose level will occur only after all subjects in the previous cohort have completed the full 7-week course of BKM120-CRT and have been evaluated for safety and toxicity. Safety will be evaluated based on the incidence of adverse events (AEs), physical exam findings, and clinical laboratory test results. A review of the safety data for each cohort will be conducted when all of the above data are available. In the event that an MTD is not reached after dose level 5, the study will be considered to have reached a biologically acceptable dose appropriate for Phase II study. Any further dose escalations or de-escalations will require a protocol amendment.

2) Three patients will initially be enrolled at dose level 1. The following rules apply for the advancement to the next dose level and to determine the MTD (see also Table 7). Enrollment may proceed at the higher dose according to the rules after three patients have been treated for the 2 weeks of BKM120 followed by 7 weeks of BKM120+CRT at a given dose level and safety data have been reviewed. The dose will be increased until a DLT is observed in one subject. Dose limiting toxicity is graded according to the National Cancer Institute’s CTCAE v4.0 (<http://ctep.cancer.gov/forms/CTCAEv4.pdf>).

Once a DLT occurs, additional subjects will be added to the cohort until either a second subject experiences a DLT or six subjects are treated at that dose level. If no additional subject experiences a DLT at the trigger dose-level, further dose escalation as outlined in Table 8 will be explored in cohorts of three subjects.

If two or more subjects experience a DLT at a given dose, then three additional subjects will be treated at the next lower dose, unless six subjects have already been treated at that dose.

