## **5.8 Agent Administration**

### **5.8.1 BKM120 Administration**

The study drug BKM120 will be self-administered (by the patients themselves). The investigator will instruct the patient to take the study drug exactly as specified in the protocol. BKM120 will be administered on a continuous once daily dosing schedule. Patients should be instructed to take the dose of BKM120 daily in the morning, one hour after a light breakfast (morning meal) at approximately the same time each day. BKM120 should be taken with a glass of water and consumed over as short a time as possible. Patients should swallow the capsules as a whole and not chew them. Do not crush capsule. Patients should continue to fast for 2 hours after the administration of each BKM120 dose.

If vomiting occurs during the course of treatment, no re-dosing of the patient is allowed before the next scheduled dose. The occurrence and frequency of any vomiting during a treatment must be noted as an adverse event. In addition, on the days of full pharmacokinetic sampling, the exact time of any episodes of vomiting within the first 4 hours post-dosing on that day and within the first 4 hours following the previous day's dosing must be noted whenever possible.

If the patient forgets to take her/his dose AFTER 6:00 PM, then the dose should be withheld that day and BKM120 should be restarted the following day.

Patients must avoid consumption of St. John's Wort, Seville oranges, grapefruit or grapefruit juice, grapefruit hybrids, pummelos and exotic citrus fruits from 7 days prior to the first dose of study medication and during the entire study treatment period due to potential CYP3A4 interaction with the study medication. Patients must avoid concomitant intake of strong and moderate CYP3A4/5 inhibitors and inducers. Orange juice is allowed.

All dosages prescribed and dispensed to the patient and all dose changes during the study must be recorded. If a patient requires a BKM120 dose delay of >14days from the previous dose, the patient must be discontinued from treatment but will only come off study if dead or due to refusal to continue on the study. Patients will only require a 28 day follow up visit after the last dose of BKM120.

Medication labels will comply with US legal requirements and be printed in English. They will supply no information about the patient. The storage conditions for study drug will be described on the medication label.

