## APPENDIX B: DRUGS THAT ARE PROHIBITED

- Other investigational therapies must not be used while the patient is on the study.
- Anticancer therapy (chemotherapy, biologic or radiation therapy, and surgery) other than the study treatments must not be given to patients while the patient is on the study. If such agents are required for a patient then the patient must be discontinued from the study.
- In *vitro* metabolism studies suggest that oxidative metabolism of BKM120 is predominantly mediated by CYP3A4 (fm>0.9), with only minor contributions of CYP1A1. As BKM120 is a sensitive CYP3A4 substrate, co-administration of BKM120 with strong and moderate CYP3A4 inhibitors and CYP3A4 inducers is prohibited. See below for a list of prohibited drugs. Please note this list may not be comprehensive.
- Based on in vitro studies, co-administration of BKM120 with CYP3A4 inducers is predicted to decrease the systemic exposure to BKM120, thereby increasing the risk of exposing the patient to subtherapeutic drug levels. See below for a list of prohibited CYP3A inducers. Please note that this list may not be comprehensive. Therapeutic doses of warfarin sodium (Coumadin®) or any other coumadin-derivative anticoagulants are not permitted.
- If a patient requires the concomitant use of any medication included in Table 18 below entitled “List of Prohibited QT prolonging drugs” (i.e., drugs that are generally accepted by the Qtdrugs.org Advisory Board of the Arizona CERT to have a risk of causing Torsades des de Pointes), study treatment administration must be interrupted as long as the patient requires therapy with the QT prolonging agent.
- Herbal preparations/medications are not allowed throughout the study. These herbal medications include, but are not limited to St. John’s wort, Kava, ephedra (ma huang), ginko biloba, dehydroepiandrosterone (DHEA), yohimbe, saw palmetto, ginseng. Patients should stop using these herbal medications 7 days prior to first dose of study drug.
- Hormonal contraceptives may be affected by cytochrome P450 interactions, and are therefore not considered effective in this study.

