**Table 17: LIST OF PROHIBITED CYP3A INHIBITORS AND INDUCERS**

Strong inhibitors	CYP3A	Moderate inhibitors	CYP3A	Strong inducers	CYP3A	Moderate inducers	CYP3A
clarithromycin		aprepitant		avasimibe		bosentan	
conivaptan		atazanavir		carbamazepine		efavirenz	
grapefruit juice		cimetidine		Phenobarbital (barbiturates)		etravirine	
indinavir		ciprofloxacin		phenytoin		modafenil	
itraconazole		darunavir		rifabutin		nafcillin	
ketoconazole		diltiazem		rifampin		ritonavir	
lopinavir		erythromycin		St. John's Wort		talviraline	
mibefradil		fluconazole				tipranavir	
nefazodone		tofisopam					

Strong inhibitors	CYP3A	Moderate inhibitors	CYP3A	Strong inducers	CYP3A	Moderate inducers	CYP3A
nelfinavir		verapamil					
posaconazole		amprenavir					
ritonavir		fosamprenavir					
saquinavir		elvitegravir					
telithromycin		tipranavir					
troleandomycin							
voriconazole							

This database of CYP inhibitors was compiled from the Indiana University School of Medicine’s “Clinically Relevant” Table and from the University of Washington’s Drug Interaction Database based on *in vitro* studies. Strong inhibitors are predicted to increase BKM120 AUC > 5-fold, and moderate inhibitors are predicted to increase BKM120 AUC  $\geq$  2-fold but < 5-fold.

This database of CYP inducers was compiled from the FDA’s “Guidance for Industry, Drug Interaction Studies;” from the Indiana University School of Medicine’s “Clinically Relevant” Table; and from (Pursche et al. 2008).

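### Prescription CYP3A inhibitors and inducers may be taken until the day before the first BKM120 dose, while grapefruit and St. John's wort in the same table need 7 days off: a minor safety and consistency gap

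*Combined protocol and SAP*

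**What the plan says.** Three places deal with prescription CYP3A drugs, and none gives a number of days.

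- Section 3.3, criterion 18, excludes patients on a moderate or strong CYP3A inhibitor or inducer when "the treatment cannot be discontinued or switched to a different medication prior to starting study drug".
- Section 5.8.1: "Patients must avoid concomitant intake of strong and moderate CYP3A4/5 inhibitors and inducers".
- Appendix B: "co-administration of BKM120 with strong and moderate CYP3A4 inhibitors and CYP3A4 inducers is prohibited".

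Dietary and herbal agents have a dated rule.

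- Section 3.3, criterion 17, excludes "Patients who have taken herbal medications and certain fruits within 7 days prior to starting study drug".
- Section 5.8.1 sets the same 7 days for St. John's wort and the listed citrus fruits, "due to potential CYP3A4 interaction with the study medication".
- Appendix B, on herbals: "Patients should stop using these herbal medications 7 days prior to first dose of study drug".

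The Appendix B table of prohibited CYP3A agents lists grapefruit juice as a strong inhibitor and St. John's wort as a strong inducer. They stand beside drugs such as clarithromycin, itraconazole, rifampin and carbamazepine. The note under the table says: "Strong inhibitors are predicted to increase BKM120 AUC > 5-fold". The QT-drug table in the same appendix also has a dated start, since its ban runs from screening.

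**The concern.** The reason given in 5.8.1 for the 7-day rule applies equally to the prescription drugs in the table, yet those drugs may be stopped the day before Day 1. Stopping a drug does not end its effect on the enzyme at once. BKM120 is described as a sensitive CYP3A4 substrate, so the first days of dosing could run above or below the exposure that the assigned level is meant to test.

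Those days fall in the 2-week BKM120-alone lead-in. The optional biopsy at 7 to 10 days, which serves the single-agent activity objective, falls there too. Cohorts start at three patients, and section 5.3 states: "Any subject who receives at least one dose of the study drug (BKM120) will be included in analysis for DLT". An avoidable exposure shift in one patient therefore enters a dose decision.

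**Working it through.** **1. Inputs from the documents.** Section 2.2.8.8: BKM120 effective half-life 38 to 49 h; accumulation ratio at 100 mg of 2.7 (day 8) and 3.3 (day 28); exposure down about 45-50% with an enzyme inducer; exposure CV about 36% at 100 mg. Appendix B: strong inhibitors raise AUC more than 5-fold, moderate ones from 2-fold to under 5-fold. Table 8: BKM120 at 20, 40, 60, 80 and 100 mg. Section 5.3: 14 days alone plus 49 days with CRT, 63 days in all.

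**2. The plan's own figure.** Accumulation = 1/(1 - 2^(-24/half-life)). This gives 2.82 at 38 h and 3.47 at 49 h; the reported 3.3 corresponds to 46.1 h. The stated half-life and accumulation agree, so a one-compartment model is a fair basis.

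**3. Carry-over model.** Once-daily dosing for 63 days, half-life 38 h. The remaining share of the interaction is r = 2^(-(t + W)/h), where t is hours from the first BKM120 dose, W the gap since the last interacting dose, and h the offset half-life. The documents give no h, so a range is shown. Relative clearance is 1/(1 + 4r) for a 5-fold inhibitor, 1/(1 + r) for a 2-fold inhibitor, and 1 + r for an inducer that halves exposure.

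Example, 5-fold inhibitor, W = 24 h. At h = 12 h, r starts at 0.25 and falls to 0.06 a day later. At h = 72 h, r starts at 2^(-24/72) = 0.794, so clearance starts at 1/(1 + 3.175) = 0.24 of normal and recovers slowly.

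**4. Exposure relative to no interaction (lead-in / all 63 days), last dose 24 h before.**

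| Offset half-life | 5-fold inhibitor | 2-fold inhibitor | 2-fold inducer |
|---|---|---|---|
| 12 h | 1.02 / 1.00 | 1.01 / 1.00 | 0.99 / 1.00 |
| 24 h | 1.09 / 1.02 | 1.03 / 1.01 | 0.97 / 0.99 |
| 48 h | 1.30 / 1.06 | 1.09 / 1.02 | 0.91 / 0.98 |
| 72 h | 1.52 / 1.12 | 1.16 / 1.04 | 0.85 / 0.97 |
| 168 h | 2.03 / 1.41 | 1.35 / 1.12 | 0.72 / 0.90 |

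**5. Yardstick.** Upward steps from 40 mg: 60/40 = 1.50, 80/60 = 1.33, 100/80 = 1.25. Downward from 100 mg: 0.80, 0.75, 0.67, then 20/40 = 0.50. In the lead-in, a 5-fold inhibitor passes the smallest upward step at a 48 h offset and the 40-to-60 mg step at 72 h. The inducer passes the smallest downward step at 168 h, not at 72 h.

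**6. Sensitivity.** At a 49 h half-life the 5-fold lead-in ratios are 1.27 (48 h) and 1.45 (72 h), and the inducer ratios 0.86 (72 h) and 0.73 (168 h). A separate calculation with a 45 h half-life and 90% of clearance by CYP3A4 gave 1.64 for a 5-fold inhibitor and 0.87 for a 2-fold inducer at 72 h. Five-fold is the floor of the strong class: in that calculation an 8-fold inhibitor reached 1.28 in the lead-in at a 24 h offset, and 1.38 over 63 days at 72 h.

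**7. With a 7-day gap (W = 168 h, half-life 38 h).** Lead-in ratios for the 5-fold inhibitor become 1.00, 1.05, 1.16 and 1.68 at offsets of 24, 48, 72 and 168 h. For the inducer they become 0.96 at 72 h and 0.82 at 168 h.

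**The case against.** The strongest reply is that little follows from the gap. The drug must be stopped, co-administration is banned, section 5.10 records medications from the prior 4 weeks, and the investigator reviews eligibility. Few patients are likely to be affected, though the documents give no number. The group is narrowed by the exclusions for HIV, uncontrolled infection and angina needing medication, and by the 6-week no-change note for psychotropics in criterion 8. At offsets of 12 to 72 h the 63-day shift is small against an exposure CV of about 36%. Levels 1 to 3 all use 40 mg BKM120, so those escalations change only cisplatin. At 40 mg, the highest modelled single-day exposure for a 5-fold inhibitor at a 72 h offset is 1.63 times steady state, or about 65 mg, below the 100 mg single-agent MTD; tolerability with CRT is not known. All of this stands and keeps the point minor.

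Criterion 17 also covers herbals such as ephedra and saw palmetto, so it is partly a general herbal rule. That does not remove the inconsistency, because 5.8.1 names CYP3A4 as the reason for the citrus fruits and St. John's wort.

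A reader might infer three stronger things that the documents do not support.

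- **That the MTD would be wrong.** The plan's escalation probability at a 20% DLT rate is (0.8)^3 + 3(0.2)(0.8)^5 = 0.709, matching its 0.71. Giving one of the first three patients an assumed 30% risk lowers it to (0.7)(0.64) + [(0.3)(0.64) + (0.32)(0.7)](0.512) = 0.661. The 30% is arbitrary: no section links BKM120 exposure to DLT risk.
- **That carry-over equals treatment at another dose level.** A dose step lasts the whole course; carry-over fades, so a lead-in shift of step size is not equivalent.
- **That 14 days is needed for long-half-life drugs.** The protocol's own standard supports 7 days. A cut on drug half-life would also treat it as the offset of the enzyme effect, and the two need not match, particularly for inducers.

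**Conclusion.** The point holds as a minor safety and consistency gap. The missing interval is plain from the text, and the protocol applies a stricter rule to two agents in the same table for a reason that covers the rest.

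Confidence in the size is lower. It depends on assumed offset half-lives, a one-compartment model and a last dose 24 h before Day 1. On those assumptions fast-offset drugs hardly matter. Slow-offset strong inhibitors, and the slowest inducers, can move lead-in exposure by more than a dose step, with a much smaller shift over the full course except at the slowest offsets. No effect on the MTD is shown, and none should be claimed.

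**What to change.** Reword criterion 18, section 5.8.1 and Appendix B so that every strong or moderate CYP3A inhibitor or inducer listed in Appendix B must be stopped at least 7 days before the first BKM120 dose. Check the last-dose date at eligibility against the 4-week medication record in section 5.10. Leave listed psychotropics under the criterion 8 note, which does not allow changes in the preceding 6 weeks. A longer interval for slow-offset agents can be left to the investigator, since 7 days does not fully clear them.

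The cost is wording in three places and one checklist line, using history already collected. A few patients may start treatment up to a week later if the drug is not stopped early in screening. That matters in a curative-intent setting where chemoradiation already follows a 2-week lead-in. Seven days fits within the 3-week baseline window in section 10 if the drug is stopped early, but that window limits the age of baseline tests and is not a planned wait.

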### **3.4 Inclusion of Women and Minorities**

Both men and women of all races and ethnic groups are eligible for this trial.

### 3.5 Screening

After consent, patients will undergo screening/baseline testing outlined in table 17. Details of the procedures can be found in section 5.12.

## 4. REGISTRATION PROCEDURES

### 4.1 General Guidelines for DF/HCC and DF/PCC Institutions

Eligible participants will be registered with the DF/HCC Quality Assurance Office for Clinical Trials (QACT) central registration system. Registrations must occur prior to the initiation of therapy. Any participant not registered to the protocol before treatment begins will be considered ineligible and registration will be denied.

An investigator will confirm eligibility criteria and a member of the study team will complete the QACT protocol-specific eligibility checklist.

Following registration, participants may begin protocol treatment. Issues that would cause treatment delays should be discussed with the Overall Principal Investigator (PI). If a participant does not receive protocol therapy following registration, the participant's registration on the study may be canceled. Notify the QACT Registrar of registration cancellations as soon as possible.

### 4.2 Registration Process for DF/HCC and DF/PCC Institutions

The QACT registration staff is accessible on Monday through Friday, from 8:00 AM to 5:00 PM Eastern Standard Time. In emergency situations when a participant must begin treatment during off-hours or holidays, call the QACT registration line at [contact] and follow the instructions for registering participants after hours.

The registration procedures are as follows:

- Obtain written informed consent from the participant prior to the performance of any protocol specific procedures or assessments.
- Complete the QACT protocol-specific eligibility checklist using the eligibility assessment documented in the participant's medical record and/or research chart. **To be eligible for registration to the protocol, the participant must meet all inclusion and exclusion criterion as described in the protocol and reflected on the eligibility checklist.**
- Fax the eligibility checklist(s) and all pages of the consent form(s) to the QACT at [contact]. For Phase I protocols, attach participant dose level assignment confirmation from the sponsor.
- The QACT Registrar will (a) review the eligibility checklist, (b) register the participant on the protocol, and (c) randomize the participant when applicable.
- An email confirmation of the registration and/or randomization will be sent to the Overall PI, study

coordinator and treating investigator and registering person immediately following the registration and/or randomization.

